**Version Date: 09/11/2017**

**Background and Aims:** Young people screened in late adolescence report surprisingly high rates of mood elevation or 'hypomanic' experience (Calabrese et al., 2003; Chandler et al., 2008). These experiences are characterized by intermittent periods of heightened activity, sleeplessness and reward-focused thinking. These experiences are also associated with increased risk of mental health problems, especially depression and anxiety (Calabrese et al., 2003). Even individuals who report these experiences but do not meet criteria for bipolar disorder show some of the same problems in cognitive and emotional function as individuals who do meet diagnostic criteria (Chandler et al., 2008; Rock et al., 2010). This strongly suggests that intermittent mood elevation per se in young people constitutes a trait marker for vulnerability to psychological disorders as a bipolar phenotype (BPP).

Individuals with the "bipolar phenotype" (BPP), defined as episodes of mood elevation and heightened activity, are at risk for several psychiatric disorders, including problem use of drugs and alcohol. Mood elevation has been linked to heightened alcohol consumption and alcohol use disorders. Individuals with BPP show elevated lifetime prevalence of alcohol use disorders (between 39%-61%), figures that exceed those reported in both major depression and schizophrenia (Regier et al., 1990; Kessler et al., 1997). Recently, we demonstrated in a controlled laboratory study that individuals with BPP report damped responses to a single dose of alcohol, compared to placebo (Yip et al., 2012). Notably, these individuals were tested at ages 18 and 19, before they had extensive exposure to alcohol and other recreational drugs, suggesting that their responses reflect an underlying neurobiological risk factor. In addition, another recent study found that a genetic polymorphism associated with susceptibility to Bipolar Disorder was also associated with damped neural responses to reward in healthy volunteers, using fMRI (Trost et al., 2016). These findings raise the possibility that individuals with BPP will exhibit damped responses to *other* rewarding stimuli, including damped feelings of well-being or euphoria from amphetamine, or less pleasurable experiences with a sweet taste.

In the present study, we will extend our previous findings and determine whether individuals with this phenotype also experience less positive effects from two other rewards: feelings of well-being from a single oral dose of d-amphetamine and preference for sweet solutions. This would suggest a mild dysfunction of the reward circuits in BPP individuals, possibly related to mesolimbic dopamine function.

**Study Aim: To compare the rewarding effects of d-amphetamine (10 and 20 mg) and sweet tastes in young adults with low and high bipolar phenotypes.** The rewarding effects of d-amphetamine in young adults will be measured using subjective self-report measures of euphoria and arousal. We will also obtain psychophysiological measures to provide an objective index of positive emotional responses. Based on our previous findings suggesting individuals with BPP display damped subjective responses to alcohol, we hypothesize that individuals

with BPP, compared to matched controls without these symptoms, will be hypo-reactive to both amphetamine reward and sweet taste reward.

## Method

**Subject Recruitment and Screening:** We will recruit 48 healthy men and women, aged 18 or 19. This age range matches the age of our previous study with alcohol, and minimizes the confounding influence of habitual alcohol consumption. Potential participants will complete the standardized Mood Disorders Questionnaire (MDQ)(Hirschfeld et al., 2000; Hirschfeld et al., 2003). We will recruit an even distribution of participants with higher or lower MDQ scores, totaling 48 individuals. Potential participants will be recruited either through our regular recruitment process (Protocol 13681B), or through targeted ads in which they are invited to complete the MDQ online. We will add the MDQ to our primary recruitment and screening protocol, and participants will come into lab for the in-person screening interview, under Protocol #13681B, which includes an EKG, physical exam, and clinical psychiatric interview.

**Screening assessments:** During the in-person screening interview, participants will be screened by a clinical psychologist and will complete several standardized questionnaires. They will undergo a semi-structured Clinical Interview for DSM-5 (SCID-5) (First, 1995) to exclude any major DSM-V psychiatric illness — including alcohol and substance abuse/dependence — with the exception of bipolar II or NOS for BPP participants. Other exclusion criteria will include: (i) any current psychotropic medication; (ii) any current non-psychotropic medication that might interact with amphetamine; (iii) history of cardiac or liver disease; (iv) high blood pressure; (v) night-shift work; (vi) more than 3-4 alcohol drinks per day for males and 2-3 drinks per day for females.

**Group matching:** As we enroll participants we will attempt to match the BPP and Healthy Control (HC) groups for sex, age, drug use history, and (non-verbal) cognitive ability (Raven et al., 1998).

**Drugs:** Oral d-amphetamine at 10mg and 20mg (Dexedrine; GlaxoSmithKline, Research Triangle Park, NC; 5mg tablets) will be placed in size 00 capsules with dextrose filler. Placebo capsules will contain dextrose only.

**Self-report subjective measures:** Subjective responses to amphetamine will be assessed using standardized scales.

The Drug Effects Questionnaire (DEQ) (Johanson and Uhlenhuth, 1980). Participants use 100mm visual analog scales (VAS) to provide ratings for four questions: 'Do you feel any drug effect?' ('None at all' to 'A lot'); 'Do you like the effects you are feeling now?' ('Dislike' to 'Like very much'); 'Are you high?' ('Not at all' to 'Very'); and 'Would you like more of what you consumed, right now?' ('Not at all' to 'Very much').

The Addiction Research Center Inventory (ARCI) (Haertzen, 1966). The ARCI is a 49-item true-false questionnaire that is sensitive to psychoactive drugs. Its 5 scales are sedation (Pentobarbital-Chlorpromazine Group; PCAG), stimulant-like effects (Amphetamine; A, and Benzedrine Group; BG), somatic and dysphoric effects (Lysergic Acid; LSD), and euphoria (Morphine-Benzedrine Group; MBG).

The Profile of Mood States (POMS) (McNair et al., 1971). The 72-item POMS will be used to assess momentary mood states across 8 subscales: Anxiety, Depression, Anger, Vigor, Fatigue, Confusion, Friendliness and Elation; participants indicating how they feel

at that moment in relation to 72 adjectives on a 5-point scale from 'Not at all' (0) to 'Extremely' (4).

**Psychophysiology:** Psychophysiological measures will be obtained to provide an objective index of responses to amphetamine and differences between the groups. Resting heart rate (HR) will be measured at 1000Hz before amphetamine and then for 2min at set intervals using a Biopac multi-channel device (MP150-BIOPAC Systems Inc., Goleta, CA). Recordings will be wireless via a (Biopac) BioNomadix RSP, (Biopac) ECG amplifier and (Biopac) BioNomadix respiration transducer while participants are seated with eyes closed. We will use disposable pre-jelled Ag-AgCl snap disposable vinyl electrodes placed in a modified Lead II configuration. Data analysis will proceed with AcqKnowledge v4 software. ECG signal will be converted to R-wave intervals (as interbeat intervals (IBI) to the nearest millisecond) and IBI values will be converted to beats per minute. Respiratory sinus arrhythmia (RSA) will be derived as a noninvasive index of cardiac vagal tone, or parasympathetic activity using the peak-valley method (Grossman and Taylor, 2007). Maximum HR expressed as milliseconds IBI during the expiration window will be subtracted from the minimum HR during the inspiration window of the respiration cycle to yield RSA (ms)(Grossman et al., 1990).

**Study environment:** The study will be conducted in the Human Behavioral Pharmacology Laboratory at The University of Chicago in secure, comfortable testing rooms. Medical assistance is readily available in the unlikely event of adverse drug experiences.

**Consent Procedures:** After screening, subjects will attend an orientation session in which they read and sign the consent form. Participants will be told that the study purpose is to investigate the effects of psychoactive drugs and food tastes on mood and behavior, and that they might receive a stimulant (such as amphetamine), a sedative (such as Valium) or an inactive placebo. Participants will agree not to use any drugs except for their normal amounts of caffeine for 24hr before and 6hr following each study visit. They will be informed that urine tests for stimulants, opioids and cannabis, breath samples for alcohol use, and pregnancy tests for women will be taken at the start of each visit and that positive tests may result in dismissal. Participants will be instructed to fast on the morning of the visit.

**Orientation:** During an initial orientation session, the study procedures will be explained, subjects will provide informed consent, and then practice study tasks. After practicing the study tasks, the participants will complete the following questionnaires: the Quick Inventory for Depressive Symptomatology (QIDS) (Rush et al., 2003); and neuroticism using the Eysenck Personality Questionnaire's Neuroticism subscale (EPQ-N)(Eysenck et al., 1985), and the cognitive ability assessment: Wechsler Abbreviated Scale of Intelligence-Second Edition (Wechsler & Hsiao-pin, 2011; WASI-II). For comparison to other studies, subjects will also complete the Lifetime Drinking History — Interview (Jacob et al., 2006) and the Timeline Follow-Back method (Sobell & Sobell, 1992; Hoeppner et al., 2010). Finally, participants will complete the revised Three Factor Eating Questionnaire (TFEQ) (de Lauzon et al., 2004), an 18-item questionnaire on eating attitudes and behaviors, with subscales to measure cognitive restraint, uncontrolled eating and emotional eating.

**Design & procedure:** Following orientation, participants will complete three 4-hour drug study visits and a final 1-hour visit. The 4-hour sessions will be conducted between 9am and 1pm separated by at least 48 hours in a double-blind, placebo-controlled, cross-over, within-subjects design. During these visits, they will consume capsules containing 10 or 20 mg d-amphetamine or placebo, double-blind in counterbalanced order. Women not using oral contraceptives will only be tested during the follicular phase (White et al., 2002).

Upon arrival at the laboratory, participants will provide BrAL and compliant urine tests for recent drug or alcohol use, and pregnancy (in females). Participants will then complete baseline questionnaires (DEQ, POMS, and the ARCI) and psychophysiological measurements. Participants will be given a snack (granola bar) to standardize food consumption, and then ingest a capsule containing placebo, 10mg or 20 mg d-amphetamine under double-blind conditions. The order will be randomized across subjects via Latin square design. Participants will complete the DEQ, POMS, and the ARCI scales at 30, 60, 90, 120, 150, 180, 210 and 240min time-points; HR will be taken at the same time. At 1pm, participants will complete a final set of questionnaires to collect their final state and subjective responses before being discharged to go home.

**The Sweet Taste Test:** On the final 1-hour study visit, participants will complete the sweet taste test and then the study will be explained. After BrAL and drug compliance tests, participants will complete the validated sweet taste test (Weafer et al., 2014). In this test, participants rate the sweetness intensity and liking of Kool-aid solutions of various sucrose concentrations.

Participants will rate five concentrations equivalent to the molar sucrose concentrations typically used in sweet taste liking procedures (i.e. 0.05, 0.10, 0.21, 0.42 and 0.83M). The test will consist of five blocks, in which each of the five solutions will be presented in random order (i.e. a total of 25 taste trials). On each presentation, participants will receive a 2ml serving of solution in a small opaque cup, instructed to swish the solution for 5s and then spit it out. They rate the sweetness of the taste (from 'Not sweet at all' to 'Extremely sweet') and their liking of the taste (from 'Disliked very much' to 'Liked very much') on two 100-mm visual analog scales. Between trials, subjects will rinse and spit a small amount of water. Sweetness and liking ratings will be calculated by averaging ratings for each solution across the five presentations.

**Data analysis and interpretation:** First we will ensure that the BPP and HC groups are matched for demographic variables, and covariates will be identified if needed. Primary outcome measures will be the stimulant (A scale) and euphoria (MBG) subscales of the ARCI (Haertzen, 1966) and the Friendliness and Elation subscales of the POMs (McNair et al., 1971). These measures will be tested using GLMs with predictors of group (BPPs vs HCs), gender, treatment (placebo, 10mg and 20mg amphetamine) and time (0, 30, 60, 90, 120 and 150 and 180min). Sweet 'liking' responses will be tested using a GLM with the predictors of group, gender and concentration (i.e. 0.05, 0.10, 0.21, 0.42 and 0.83M). Participants will be classified as sweet-likers if their liking ratings were greatest for the highest concentration solution (0.83 M); all other participants will be classified as sweet-dislikers (Weafer et al., 2014).  $\chi^2$ -tests will test the supplementary prediction that there are more sweet-likers in the BPP group than in the HC groups.

**Sample size:** Estimations of sample/group size have been derived from our previous demonstration of blunted subjective response to alcohol in BPP compared to HC males (Yip et al., 2012). In that study, the effect sizes ( $f^2$ ) for the two DEQ sub-scales of 'Feel high' and 'Feel effects' was 0.73 and 0.60, respectively. Taking the midpoint of these 2 values as our anticipated effect size (0.67), N=48 subjects would provide over 81% power (with  $\alpha = .05$ ) to detect treatment differences between BPP individuals and HC individuals.

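### The RSA sentence reverses the subtraction on the IBI scale and confuses heart-rate extremes with IBI extremes, so as written it does not give the peak-valley index it names

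*Combined protocol and SAP*

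**What the plan says.** The Psychophysiology paragraph of the Method section introduces these recordings with a stated purpose: "Psychophysiological measures will be obtained to provide an objective index of responses to amphetamine and differences between the groups". The ECG is reduced to R-wave intervals in milliseconds (IBI), and for heart rate "IBI values will be converted to beats per minute".

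RSA is then said to be "derived as a noninvasive index of cardiac vagal tone, or parasympathetic activity using the peak-valley method". The next sentence is the only operational definition in the document: "Maximum HR expressed as milliseconds IBI during the expiration window will be subtracted from the minimum HR during the inspiration window" of the respiration cycle, giving RSA in ms. There is no sign convention, absolute value or worked example.

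The section on data analysis and interpretation does not mention RSA. It says "Primary outcome measures will be the stimulant (A scale) and euphoria (MBG) subscales of the ARCI", together with two POMS subscales, and it specifies models for those measures and for sweet liking. The sample size is built on DEQ effect sizes.

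**The concern.** A peak-valley index of vagal tone should rise as the respiratory swing in IBI gets larger. The sentence puts the inspiration term first and takes the expiration term away from it, which is the opposite order. It also speaks of maximum and minimum HR while giving the result in milliseconds of IBI. The two scales run in opposite directions: the highest heart rate is the shortest IBI. The words therefore allow two different calculations, and neither is longest expiratory IBI minus shortest inspiratory IBI.

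What is at stake is the direction, and possibly the content, of one of the two physiological measures that the paragraph describes. RSA is meant to show objectively how amphetamine acts and how the groups differ, so the sign of a drug or group contrast carries meaning. Two analysts following the sentence in good faith could also produce different variables.

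**Working it through.** The documents state no RSA value, so there is no figure to reproduce. The check is of the formula.

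**Inputs from the protocol (Method, Psychophysiology).** Subtracting X from Y means Y - X, so RSA = [minimum, inspiration] - [maximum, expiration], in ms. The named method is peak-valley.

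**Assumptions, not from the documents.** IBI is longer in expiration than in inspiration. For the model breath, IBI is sinusoidal with mean 850 ms and amplitude A (swing 2A). Inspiration is the first half of the breath, and the shortest IBI falls at a fraction L of the breath, between mid-inspiration (L = 0.25) and end-inspiration (L = 0.5).

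**Step 1: maximum and minimum read as IBI.** This is the likelier reading, because the result is in ms.

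- As written: min IBI(insp) - max IBI(exp).
- Peak-valley: max IBI(exp) - min IBI(insp).

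One is exactly minus the other. The written form can be positive only if every inspiratory IBI exceeds every expiratory IBI.

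| A (ms) | As written (ms) | Peak-valley (ms) |
|---|---|---|
| 20 | -40 | +40 |
| 50 | -100 | +100 |
| 100 | -200 | +200 |

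These values are the same at L = 0.25, 0.375 and 0.5. A larger swing gives a lower score.

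**Step 2: effect on contrasts under the IBI reading (illustrative swings).** Suppose the swing falls from 100 to 60 ms in one group and from 100 to 80 ms in a second, blunted group.

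- Peak-valley changes: 60 - 100 = -40 and 80 - 100 = -20. Difference (second minus first): -20 - (-40) = +20.
- Changes as written: -60 - (-100) = +40 and -80 - (-100) = +20. Difference: 20 - 40 = -20.

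Every signed contrast reverses. The ratio of the two responses is 20/40 = 0.5 either way. Multiplying an outcome by -1 negates each coefficient and leaves its standard error alone. In a simulated comparison of 24 against 24 (assumed means 100 and 80, SD 30), t was 4.06 before the flip and -4.06 after it, with p = 0.00019 both times.

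**Step 3: HR read literally.** Maximum HR in expiration is the shortest expiratory IBI, and minimum HR in inspiration is the longest inspiratory IBI. The rule becomes max IBI(insp) - min IBI(exp). In the model breath this equals -2A cos(2πL). With A = 50, so the true swing is 100 ms throughout:

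| L | HR reading (ms) | Peak-valley (ms) |
|---|---|---|
| 0.25 | 0 | 100 |
| 0.3125 | 38 | 100 |
| 0.375 | 71 | 100 |
| 0.4375 | 92 | 100 |
| 0.5 | 100 | 100 |

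The score moves across the whole range while the swing stays fixed. It mixes respiratory timing with the size of the swing, and changing its sign does not repair it.

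**The case against.** The strongest reply is that this is a drafting slip. The paragraph names a recognised method, cites sources for it, names the analysis software and gives the unit, so the intended quantity is plain enough. RSA values that were nearly all negative would be noticed at the first data check. If the IBI reading were carried through, a uniform sign change loses nothing and can be undone. RSA is not a primary outcome, does not enter the sample size, and has neither a specified model nor a directional hypothesis of its own.

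Most of this stands, and it sets the size of the point. It does not make the sentence right: naming the method shows the intent, and the explicit formula contradicts it. The data check offers less protection on the HR reading, which in the model gives zero or positive values that could pass as ordinary RSA.

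A reader might infer more than the text supports:

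- **That every normal breath would score negative.** This holds on the IBI reading only.
- **That every RSA effect is reported the wrong way round.** The document is a plan and reports no RSA result. The reversal would follow only if the sentence were implemented as typed, on the IBI scale.
- **That a blunted group would look exaggerated.** It would not. In Step 2 the second group still shows half the response of the first.
- **That heart rate is compromised too.** Heart rate is obtained separately, by converting IBI to beats per minute, and this formula does not touch it.

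**Conclusion.** The point holds as an error in a stated computing rule, with limited impact. On the IBI reading, the rule returns minus the peak-valley value. The direction of signed RSA contrasts would be reversed, with magnitudes and two-sided p-values unchanged. On the literal HR reading, it uses the wrong extremes and no longer measures the swing. The wording does not settle which calculation is meant, and neither is the index of vagal tone that the paragraph describes.

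The conclusion rests on IBI being longer in expiration than in inspiration, which is ordinary physiology but is not stated in the protocol. The millisecond values are illustrative. The effect is confined to RSA, a supporting measure; no planned primary analysis depends on it.

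**What to change.** Replace the sentence with: RSA (ms) = longest IBI in the expiration window minus shortest IBI in the inspiration window; higher values mean greater RSA. Delete the words 'HR expressed as', so that only the IBI scale is used.

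The cost is one sentence in the protocol and no new data. If RSA has already been derived, check which calculation was used. Values from the IBI reading need only be multiplied by -1. Values from the HR reading must be recomputed from the stored IBI and respiration recordings.

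### The primary model for this three-session cross-over has no session term, and dose order is not said to be allocated within BPP and HC, which can cost precision on the group-by-dose contrast

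*Combined protocol and SAP*

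**What the plan says.** The Design & procedure paragraph of the Method section says that "participants will complete three 4-hour drug study visits and a final 1-hour visit". The drug visits are "separated by at least 48 hours in a double-blind, placebo-controlled, cross-over, within-subjects design". Dose order is described twice, as "double-blind in counterbalanced order" and then as "The order will be randomized across subjects via Latin square design". The sequences are not listed and the number of squares is not given. Nothing says whether order is allocated within each group. At every session, before the capsule, "Participants will then complete baseline questionnaires (DEQ, POMS, and the ARCI) and psychophysiological measurements".

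On numbers, the recruitment paragraph says "We will recruit an even distribution of participants with higher or lower MDQ scores, totaling 48 individuals", which I read as 24 per group. The group-matching paragraph covers sex, age, past drug use and cognitive ability; dose order is not among the matching factors.

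The data-analysis paragraph tests the primary ARCI and POMS scales with "GLMs with predictors of group (BPPs vs HCs), gender, treatment (placebo, 10mg and 20mg amphetamine) and time". The time levels run from 0 to 180 minutes, so time means minutes within a session. No session (period) or sequence term is listed.

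**The concern.** The hypothesis is that BPP participants respond less to amphetamine than controls, so the group-by-treatment contrast carries the study. The outcomes are self-reports, and participants are told that they may receive a stimulant, a sedative or placebo. Ratings could plausibly drift from the first session to the third as the setting becomes familiar.

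In a three-period cross-over such a drift is usually removed by a session factor. Without one it has two effects. It inflates the within-participant error. Where the two groups happen to receive the doses in different orders, it also moves the group-by-treatment contrast in that trial. With 24 per group there is little precision to spare.

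**Working it through.** The plan gives no figure for session effects or order balance, so there is no stated figure to reproduce on this point.

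**Inputs from the protocol.** Three treatments in three sessions; N = 48, read as 24 per group; Latin-square order; the model terms listed above.

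**Assumptions (not in the protocol).** One square, hence 48/3 = 16 participants per order. Residual SD of a participant's session score is 1. A linear trend of δ = 0, 0.5 or 1 residual SD per session, equal in both groups. Participant differences are removed by the model.

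**1. Chance imbalance in order.** If order ignores group, the number K of placebo-first participants among the 24 BPP participants is hypergeometric (48 in total, 16 placebo-first, 24 drawn). The groups differ by |2K − 16|.
- P(difference ≥ 4) = 0.36
- P(difference ≥ 6) = 0.12
- P(all three orders split exactly 8/8/8) = C(16,8)³ / C(48,24) = 0.066

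**2. How a trend enters the contrast.** Let D be the session number of 20 mg minus that of placebo. Over the three orders of one square D is +2, −1, −1. Its mean is 0, so with equal filling the trend cancels from the pooled dose contrast. Its mean square is (4 + 1 + 1)/3 = 2. A participant's 20 mg minus placebo contrast therefore has variance 2 + 2δ² when session is ignored. For the difference between groups of 24:

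SE = √[ (2/24) × (2 + 2δ² × 48/47) ]

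The factor 48/47 arises because the 48 order slots are fixed in number.

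| Trend δ | SE, no session term | SE, session term |
|---|---|---|
| 0 | √0.1667 = 0.41 | 0.41 |
| 0.5 | √(0.1667 + 0.0426) = 0.46 | 0.41 |
| 1 | √(0.1667 + 0.1702) = 0.58 | 0.41 |

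Simulation with order not stratified by group agrees with these values to within about 0.01.

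**3. Error rates, order not stratified by group.** Simulated type I error without the session term is about 5% at all three trends. Power for a true group difference of 1 SD is roughly Φ(1/SE − 1.96), which gives 69%, 59% and 41%. Simulation with t-tests gives about 67%, then 57–60%, then 39–42%, depending on the error term used. With the session term it stays at about 65–68% throughout.

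**4. Order balanced within group, session still omitted.** The trend now cancels from the estimate, so the true SE is 0.41. The model still counts the trend as error and reports √[(2/24)(2 + 2δ²)] = 0.58 at δ = 1, too large by a factor of √2. The nominal 5% test then rejects with probability 2 × P(t with 46 df > 2.013 × 1.414) = 0.7%. At δ = 0.5 the figure is 2.9%. Balancing alone therefore does not recover the lost power.

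**5. What six orders would and would not do.** Assume true effects of 0, 0.5 and 1 for placebo, 10 mg and 20 mg, with carry-over a fraction of the previous session's effect.

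| Carry-over | Contrast | One square | Six orders | True |
|---|---|---|---|---|
| 10% | 10 mg − placebo | 0.433 or 0.533 | 0.483 | 0.5 |
| 30% | 10 mg − placebo | 0.30 or 0.60 | 0.45 | 0.5 |
| 10% | 20 mg − placebo | 0.967 | 0.967 | 1 |
| 30% | 20 mg − placebo | 0.90 | 0.90 | 1 |

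Six orders average the carry-over shift without removing it, and leave 20 mg minus placebo unchanged. They do make adjustment cheaper. With n = 24, adding first-order carry-over terms raises the variance of 20 mg minus placebo from 0.083σ² to 0.417σ² in one square (efficiency 0.083/0.417 = 20%), but only to 0.104σ² with both squares (80%).

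**The case against.** A reader might infer more than this from the words Latin square: that only three orders are used, that each dose always follows the same predecessor, that order is unbalanced between BPP and HC, and that carry-over and session effects therefore bias the dose contrasts. The documents do not support that.
- Counterbalanced Latin-square order fits both mirror-image squares as well as one. Even in one square, a dose given first has no predecessor.
- On balance within group the protocol is silent; it does not rule balance out.
- An additive session effect cancels from pooled dose contrasts when the orders are equally filled.
- Carry-over common to both groups cancels from group-by-dose when the groups have the same mix of orders.
- The minimum 48-hour gap and the pre-capsule baseline at each session both limit carry-over, and nothing in the documents shows its size.

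All of that stands. It is also fair to say that chance imbalance averages to zero and leaves the type I error near 5%, so the validity of the test is not in question.

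The baseline is a further partial defence. Time 0 is in the model, so a session shift already present before the capsule can be separated from the response to it. A trend in the response itself, for example a fading effect of novelty after dosing, cannot be separated in this way. None of these arguments replaces the missing session term.

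**Conclusion.** The point holds as a loss of precision. The stated primary model leaves a known design factor in the error term, and the protocol does not say that order is allocated within group. Without both measures, the standard error of the group difference in 20 mg minus placebo rises from about 0.41 to 0.46 at a trend of 0.5 residual SD per session, and to 0.58 at 1 SD. Power for a 1 SD difference falls from about 67% to about 58–60% or 39–42%. If there is no session trend, nothing material is lost.

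These sizes rest on 24 per group, full completion, one square, and a linear trend that is equal in both groups. The protocol gives no information on the trend, so the range matters more than any single figure. Bias from carry-over, a single square, or order that is in fact unbalanced are not established by the documents and form no part of this conclusion.

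**What to change.** Make two changes, together:
- Add session number (1, 2, 3) as a factor in the primary model. If the decisive test is an interaction with time within session, include session by time as well.
- State that dose order is allocated in equal numbers within BPP and within HC, and list the sequences.

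Using both mirror-image squares is optional. With 24 per group, six orders give 24/6 = 4 participants per order in each group. This evens out which dose precedes which and makes any later carry-over adjustment cheaper, but it does not by itself remove carry-over bias.

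The session factor costs 2 degrees of freedom. Session by time, if needed, costs a further 2 × (7 − 1) = 12 over the seven listed time points. Otherwise the cost is a stratified randomisation list and a sentence or two of text. Visits and sample size do not change, and the data needed are already collected.

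### Does a 240-minute assessment in a 9am to 1pm session, with the capsule given only after set-up, undermine the trial's analysis?

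*Combined protocol and SAP*

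**What the plan says.** All of this is in the Method section of the combined protocol and SAP.

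- **Session hours** (Design & procedure): "The 4-hour sessions will be conducted between 9am and 1pm".
- **Before the capsule**: urine, breath and pregnancy tests come first; under Consent Procedures, "pregnancy tests for women will be taken at the start of each visit". Next, "Participants will then complete baseline questionnaires (DEQ, POMS, and the ARCI) and psychophysiological measurements". A snack is then given "to standardize food consumption, and then ingest a capsule containing placebo, 10mg or 20 mg d-amphetamine".
- **After the capsule**: "Participants will complete the DEQ, POMS, and the ARCI scales at 30, 60, 90, 120, 150, 180, 210 and 240min time-points". Heart rate is taken at the same times.
- **End of session**: "At 1pm, participants will complete a final set of questionnaires to collect their final state and subjective responses before being discharged to go home".
- **Analysis** (Data analysis and interpretation): the model for the four primary subscales has seven time levels, every 30 minutes from 0 to 180. The 210- and 240-minute points are not among them, and no other analysis is named for them.

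The document gives no clock time for the capsule, no length for set-up and no zero point for the minute labels. It does not say whether the 1pm set is the 240-minute assessment or an additional one.

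**The concern.** A window from 9am to 1pm holds exactly 240 minutes. If the capsule is taken some way into it, an assessment 240 minutes after the capsule cannot take place before 1pm. Set-up is clearly not instantaneous. The DEQ has four questions; for the other two scales, "The ARCI is a 49-item true-false questionnaire" and "The 72-item POMS will be used to assess momentary mood states". The baseline battery is therefore 4 + 49 + 72 = 125 items, on top of the tests, the recording and the snack.

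Read strictly, the schedule cannot be kept at any drug visit. Staff might skip the last point, take it early under a 240-minute label, or keep the participant beyond 1pm. If they chose differently from visit to visit, the late data would not be comparable. The time from capsule to discharge also comes out differently: less than 240 minutes by the session hours, at least 240 by the assessment list. If the overrun reached into the times used by the primary model, the treatment-by-time comparison would lose data.

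**Working it through.** **Inputs from the document.** Session 9:00 to 13:00; post-dose times 30 to 240 in steps of 30 (eight points); primary model times 0 to 180; 48 participants, three drug visits each.

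**Input not in the document.** Set-up time *s*, the minutes from 9:00 to the capsule. It is varied from 0 to 90 as an assumption.

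**Step 1: the plan's own figure.** 13:00 − 9:00 = 240 min, which reproduces the stated four hours.

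**Step 2: times counted from the capsule.** The latest post-capsule time that fits before 1pm is 240 − *s*. The 240-minute point falls at 13:00 + *s*.

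| *s* (min) | 240 − *s* | Last listed point that fits | Clock time of 240-min point |
|---|---|---|---|
| 0 | 240 | 240 | 13:00 |
| 15 | 225 | 210 | 13:15 |
| 30 | 210 | 210 | 13:30 |
| 45 | 195 | 180 | 13:45 |
| 60 | 180 | 180 | 14:00 |
| 90 | 150 | 150 | 14:30 |

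The 240-minute point fits only if *s* = 0. The 210-minute point fits if *s* ≤ 30, and the 180-minute point, the last in the primary model, if *s* ≤ 60.

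**Step 3: times counted from 9am.** The 240-minute point is then exactly 1pm and could be the 1pm set. The label of 30 minutes would mean 30 − *s* minutes after the capsule: +15, 0, −15 and −30 for *s* = 15, 30, 45 and 60. At *s* = 15 the schedule runs in order; from *s* = 30 the first response point is at or before dosing. The order of the text (capsule, then time points) and the time-0 level in the model favour the capsule as origin.

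**Step 4: how much is touched.** Drug visits: 48 × 3 = 144. Scheduled post-dose assessments: 144 × 8 = 1,152. For *s* above 0 and up to 30, one point per visit does not fit: 144/1,152 = 12.5%. For *s* above 30 and up to 60, two do not fit: 288/1,152 = 25%. These are shares of what is scheduled. The share entering the primary model is zero in both cases, because that model stops at 180.

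**Step 5: what the overrun does to the stated analyses.** Suppose the last assessment runs late: the 0 to 180 data are all collected. Suppose instead it is dropped: with *s* ≤ 60 the 0 to 180 data are again all collected. The sweet-taste model and the χ² test use a separate visit. The sample-size paragraph does not use the number of time points. So with *s* ≤ 60 nothing in the stated analyses differs between the two courses.

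**The case for a change.** The strongest case for acting is that the conflict at 240 minutes needs no assumed duration, only that set-up takes some time, and that it recurs at all 144 visits. Moving the origin to 9am is no clean escape: every label would then overstate time since the capsule by *s*, including the labels in the primary model. Assuming that set-up happens before 9am is not supported either, because the tests are placed at the start of a four-hour visit. The remedy would also be cheap, since it is mostly wording.

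Much of this stands. On the likelier reading the text is inconsistent, and the zero point ought to be written down. What does not stand is the weight put on it. Beyond the 240-minute point, the sizes rest on an assumed set-up time: the 25%, the capsule-to-discharge intervals in the table, and any estimate of extra staff hours. That late assessments would be lost is conjecture; nothing in the plan says a participant leaves with one outstanding. The document states no observation period after the capsule and no discharge criterion, so the discharge interval is the same clock conflict seen from the other end, not a second contradiction.

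Stopping the primary model at 180 minutes is a legitimate choice of window made in advance. Asking for a reason, or for a use for the later points, is a request for more text and does not correct an error.

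**Conclusion.** The inconsistency is real but minor, and no change to the design or analysis follows. Counted from the capsule, the 240-minute assessment overruns 1pm by the set-up time at each of the 144 drug visits, which is 12.5% of scheduled post-dose assessments. Whether the 210-minute point also overruns cannot be told from the document. None of these data enters a stated analysis, so keeping the late assessment or losing it leaves every stated test and conclusion as it was.

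This rests on two things: that times run from the capsule, and that set-up takes 60 minutes or less, or else that 1pm is not enforced as a hard stop. If set-up regularly exceeded 60 minutes and discharge were held to 1pm, the 180-minute point would be lost and the primary model would be touched; nothing in the document suggests a set-up of that length.

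What remains is clerical. The session hours, the last listed assessment, the 1pm set and the discharge time in Design & procedure must be reconciled with one another and the zero point stated. Which of those timings is right is not judged here. Analysts can fill the gap sensibly by treating minutes as time since the capsule, taking the pre-capsule battery as time 0, and fitting the model to the 0 to 180 points as planned.
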